Study Protocol and Statistical Analysis Plan

Title: The Effects of Combined Transcranial Direct Current Stimulation and Pneumatic Compression on Selected Recovery Parameters After a 10K Run

NCT Number: Pending

Ethics Committee Approval Number: 2025-17/11

Date: 16 December 2025

Objectives and Hypotheses

Research Question:

In this context, the primary research question is:

"How do transcranial direct current stimulation (tDCS), pneumatic compression (PC), and their combined application affect subjective well-being, total quality of recovery (TQR), heart rate variability (HRV), neuromuscular performance (maximal voluntary isometric contraction and vertical jump), and cognitive function (Stroop Test) in master male long-distance runners aged 40–55, immediately before, immediately after a 10-kilometer (10K) run, and following a 20-minute recovery intervention?"

Hypotheses:

- **H1:** tDCS application will significantly improve post-run recovery markers, including subjective well-being, TQR, HRV, neuromuscular performance, and cognitive function.
- **H2:** PC application will significantly improve post-run recovery markers, including subjective well-being, TQR, HRV, neuromuscular performance, and cognitive function.
- **H3:** Combined application of tDCS and PC will produce greater improvements in recovery markers compared to either intervention applied individually.

Objective:

The aim of this study is to evaluate the effects of tDCS, PC, and their combined application on physical, physiological, psychological, and cognitive recovery in master male long-distance runners after a 10K run, with the goal of shortening recovery time and preventing performance decline following intensive exercise.

Specific Aims:

- To investigate the effects of tDCS and PC and combined tDCS+PC on post-run muscle fatigue and neuromuscular performance (maximal voluntary isometric contraction and vertical jump).
- To examine changes in subjective well-being and TQR as indicators of psychological recovery.
- To assess cognitive recovery using the Stroop test.
- To analyze physiological responses by evaluating HRV following each intervention.
- To compare the individual and combined contributions of tDCS and PC to overall recovery.

Method

The aim of this study is to investigate the effects of combined tDCS and PC on recovery in master male runners following a 10K run. The study also aims to examine whether these interventions can shorten recovery time and prevent performance decline after prolonged and intense exercise.

This study will be conducted as a randomized, controlled, crossover trial using a mixed experimental design. Each participant will undergo four different recovery protocols in a randomized order, with a one-week interval between sessions. Randomization will be performed using Research Randomizer (<https://www.randomizer.org/>), assigning participants to one of four sequences (e.g., B–A–D–C). Participants will be identified only by numerical codes to ensure blinding and maintain confidentiality. Each participant will experience all protocols, allowing within-subject comparisons and minimizing order-related bias.

The four recovery protocols are:

- (A) tDCS group: transcranial direct current stimulation only
- (B) PC group: pneumatic compression only
- (C) tDCS + PC group: simultaneous application of both tDCS and PC
- (D) Control group: passive rest with no intervention

tDCS and PC interventions represent the independent variables, while dependent variables include WBQ, TQR, HRV, Stroop Test, vertical jump, and MVIC with EMG recordings.

Participants will be 35 male long-distance master runners aged 40–55, residing in Bursa, Turkey, with at least five years of consistent training. They will train five days per week, 90 minutes per day, and must meet aerobic fitness criteria established by the American College of Sports Medicine, completing official 10K race under 50 minutes within last six months and maintain a weekly running volume of 60-80 km. Volunteers will be recruited from the local long-distance running community familiar to the principal investigator, [name]. Participants will be excluded if they have used regular medications within the last six months, consumed stimulants, caffeine, or alcohol within 24 hours prior to testing, smoke, have experienced musculoskeletal injuries in the past six months, are currently undergoing physical therapy, or have neurological conditions such as epilepsy or seizure history, or possess cardiac, brain, or other electronic implants. Additional exclusion criteria include open wounds or dermatological conditions on the head, circulatory disorders such as deep vein thrombosis, peripheral arterial disease, severe varicose veins, or prior exposure to tDCS or PC interventions. Participants may withdraw voluntarily, fail to attend sessions, or be removed if cardiovascular, neurological, or orthopedic complications occur during exercise or interventions, or if they experience excessive discomfort or adverse effects from the tDCS or PC procedures. Written informed consent will be obtained after explaining the study's purpose, procedures, potential risks, and benefits. Sample size was calculated using G*Power 3.1.9.7 for repeated measures ANOVA with within-between interaction, effect size $f = 0.30$, $\alpha = 0.05$, power = 0.80, resulting in $n = 28$. Accounting for potential dropouts, 35 participants will be recruited.

Screening and Familiarization Session:

Participants will undergo anthropometric measurements (weight, body fat, height) using Tanita BC 418 MA and Seca stadiometer. Physical fitness will be evaluated with a 12-minute Cooper Test on a 400 m track under controlled conditions (temperature 20–24°C, relative

humidity 50–70%, wind \leq 10 km/h). A 20-minute warm-up including jogging, accelerations, jumps, and stretching will precede testing. Distances will be recorded with a Polar V3 GPS watch.

Participants will also complete a familiarization session with the 10K course, tDCS and PC devices, Stroop Test, MVIC, and vertical jump measurements to ensure procedural understanding.

Experimental Sessions

Pre-run Measurements (T1): Immediately prior to the 10K run, participants will complete the TQR, and the WBQ in the gym. Following this, the Polar Vantage V3 GPS-enabled watch and H10 heart rate strap will be fitted to each participant, and HRV data will be recorded for 5 minutes in a seated position.

After HRV recording, participants will perform the Stroop test under researcher supervision using a computer. Subsequently, vertical jump performance will be assessed. Participants will start from an upright standing position, perform a preliminary downward squat by flexing the knees and hips, and immediately extend the knees and hips to jump vertically. Vertical jump measurements will be performed three times with a 1-minute interval between trials, and the results will be recorded.

Following the jump assessment, participants will be fitted with an EMG device for the MVIC test. EMG signals will be recorded from the Vastus Lateralis, Rectus Femoris, and Vastus Medialis muscles during the test.

10K Run: After Test-1, participants will complete a 10K run on the athletics track at Bursa Uludağ University (BUU). The route begins and ends at the Faculty of Sports Sciences, BUÜ. Participants will have 30 minutes for individual warm-up and preparation.

The run will be performed at 75% intensity, determined using the Karvonen method, based on each participant's maximum heart rate obtained during an on-field Cooper test. Target heart rate zones will be set with a ± 5 bpm tolerance. GPS and HRV tracking will be conducted using the Polar Vantage V3 watch. Additionally, perceived exertion will be assessed verbally using the Borg-20 scale at the 5K mark and immediately after completing the run, with responses recorded by the researchers.

Post-run Measurements (T2): Immediately after completing the 10K run, the procedures conducted in Test 1 will be repeated.

Interventions:

Participants will be randomly assigned to one of four protocols:

- **(A) tDCS:** Participants assigned to the tDCS intervention will receive stimulation using the Brain Premier tDCS device. During the application, participants will be positioned in a semi-recumbent posture at approximately 45° recline, and the device will be adjusted accordingly. Anode and cathode electrodes, embedded in 5×5 cm saline-soaked sponge pads, will be placed over the F3 (left dorsolateral prefrontal cortex) and F4 (right dorsolateral prefrontal cortex) locations according to the international 10–20 EEG system. Stimulation will be delivered at a constant current intensity of 2 mA for 20 minutes.

- **(B) Pneumatic Compression (PC):** Participants assigned to the PC intervention will receive lower-limb pneumatic compression using the Normatec device. They will be positioned in a semi-recumbent posture at approximately 45° recline, and the device will be adjusted to match this posture. Compression will last for 20 minute. Specifically, the most distal chamber (cell 1, ankle level) will receive 70 mmHg pulse pressure; the intermediate chambers (cells 2–4) will receive 80 mmHg; and the most proximal chamber (cell 5) will receive 60 mmHg. Each chamber will undergo 30 seconds of pulsed compression followed by 30 seconds of static hold. Chambers will inflate and deflate sequentially from distal to proximal to create a peristaltic compression pattern. This method aims to enhance intramuscular fluid dynamics, promote venous return, and facilitate the removal of metabolic by products.
- **(C) Combined tDCS + PC:** Participants in the combined intervention group will simultaneously receive tDCS and PC for 20 minutes while positioned in a semi-recumbent posture at approximately 45° recline. tDCS will be applied via 5×5 cm saline-soaked sponge electrodes over F3 and F4 regions using the Brain Premier CE-certified device at 2 mA. Electrode contact quality will be monitored via the device interface to ensure safety and adherence to protocol parameters. PC will be applied concurrently using the Normatec device. Distal cell (cell 1) will receive 70 mmHg, intermediate cells (cells 2–4) 80 mmHg, and proximal cell (cell 5) 60 mmHg pulse pressure. Each chamber will follow 30 seconds of pulsed compression and 30 seconds of static hold, proceeding in a distal-to-proximal sequential pattern to create a peristaltic flow. This synchronized intervention aims to provide a holistic recovery effect by targeting both peripheral and central mechanisms of recovery.
- **(D) Control:** Participants in the control group will be positioned in a semi-recumbent posture at approximately 45° recline for 20 minutes without receiving any intervention. During this period, participants will remain passive in a quiet, distraction-free environment. The 45° semi-recumbent posture is consistent with the intervention groups to control for physiological variations arising from body positioning (e.g., blood flow, venous return, postural hemodynamic changes). Active recovery strategies (e.g., walking, stretching) were deliberately excluded to avoid potential confounding effects. This standardized passive rest condition allows for a valid comparison of intervention effects between groups.

Post-intervention Measurements (T3): The procedures conducted in Test 1 will be repeated immediately after the participant completes the assigned intervention protocol.

Outcome Measures:

- Subjective scales: Well-being Questionnaire, Total Quality Recovery
- Heart rate variability (HRV) and GPS
- Cognitive performance via Stroop Test
- Vertical jump height via My Jump app
- MVIC with EMG on quadriceps muscles following SENIAM protocol
- tDCS and PC applied according to standardized protocols

Statistical Analysis

Data will be analyzed with IBM SPSS 29. Normality (Shapiro-Wilk), homogeneity (Levene), and sphericity (Mauchly) will be tested. Two-way repeated measures ANOVA (4 Time \times 4 Group) will assess interactions, with Bonferroni post-hoc tests. Effect sizes will be reported using partial eta squared (η_p^2): small (>0.01), medium (>0.06), large (>0.14). Significance threshold $p < 0.05$.

This study will provide comprehensive insight into the effects of tDCS and PC, alone and in combination, on recovery in older endurance athletes, contributing evidence-based recommendations for optimizing performance and minimizing injury risk.

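### H3 needs the combination to beat both tDCS and PC, but the plan gives that pair no decision rule and no power, and Bonferroni between the two contrasts costs power that H3 need not lose

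*Combined protocol and SAP*

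**What the plan says.** Under Objectives and Hypotheses, H3 reads "Combined application of tDCS and PC will produce greater improvements in recovery markers compared to either intervention applied individually". A Specific Aim also compares the individual and combined contributions of the two devices.

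The participants paragraph under Method holds the only power statement: "Sample size was calculated using G*Power 3.1.9.7 for repeated measures ANOVA with within-between interaction", with f = 0.30, alpha 0.05, power 0.80 and a result of 28. It adds: "Accounting for potential dropouts, 35 participants will be recruited".

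Under Statistical Analysis, a two-way repeated measures ANOVA "will assess interactions, with Bonferroni post-hoc tests", at a threshold of 0.05. The Bonferroni family is not defined and the sidedness of the pairwise tests is not stated. No contrast, pairwise difference, SD, correlation or power is given for C against A or C against B. Six dependent variables are listed under Method, and none is named primary.

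**The concern.** On an ordinary reading, H3 is a claim with two required parts: C better than A, and C better than B. A significant interaction does not establish it, because the interaction can be significant merely because one device differs from rest. The 0.80 is therefore not the chance of supporting H3.

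The pairwise step does not fit H3 either. Bonferroni guards against the case where any one of several tests may be claimed. Where both tests must succeed, that guard is not needed between the two, and it lowers the chance of a true H3 being shown.

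Two misreadings could follow. With no rule, one significant contrast could be reported as support for H3. And a non-significant result from a pair with little power could be reported as no benefit of combining.

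**Working it through.** **Inputs.** From the documents: f = 0.30, alpha 0.05, power 0.80, n = 28, 35 recruited, and a crossover in which everyone receives all four conditions. Assumed, because not stated: correlation 0.5, sphericity, two-sided pairwise tests, a Bonferroni family of six pairs (0.05/6 = 0.0083), independent residuals with equal variance σ² once the participant effect is removed, and an effect at T3 only.

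**1. The plan's own figure.** For a within-between interaction with k groups and m times, λ = N·m·f²/(1−ρ), with df (k−1)(m−1) and (N−k)(m−1). With k = 4, m = 4 and ρ = 0.5:
- N = 28: λ = 28 × 4 × 0.09/0.5 = 20.16, df 9 and 72, power 0.863.
- N = 24: λ = 17.28, df 9 and 60, power 0.782.

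In steps of four, 28 is the first N to reach 0.80, so the figure reproduces as an omnibus interaction. Also 28/(1 − 0.20) = 35. With m = 3, the number of measurement times actually described (T1 to T3), power at 28 is 0.789.

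**2. False H3 rate within one outcome.** The worst case is C = A with C far above B. H3 is then wrongly supported only when C−A is significant in the favourable direction. That has probability 0.025 with each test at two-sided 0.05, and 0.05/12 = 0.004 at 0.05/6. Simulation agrees.

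The other four pairs stay at 0.05/6, and the H3 pair is read only jointly. In the worst case above, at most two of those four pairs can also be true nulls (D tied with A and C), so the familywise error is at most 0.025 + 2 × 0.0083 = 0.042. If all four conditions tie, the false H3 rate is 0.004, and the bound is 0.004 + 4 × 0.0083 = 0.037.

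**3. Joint power for H3, 28 completers.** In the crossover with three times, λ = n × (2/3) × Σ(deviation of condition effect)²/σ². Two calibrations were used:
- *Interaction power exactly 0.80:* F with df 6 and 162 needs λ = 14.16.
- *f = 0.30 taken literally:* λ = 28 × 4 × 3 × 0.09/0.5 = 60.48, where interaction power is about 1.0.

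For additive effects (D = 0, A = B = d, C = 2d) the squared deviations sum to 2d², so d/σ = √(λ/37.33). That gives 0.616 and 1.273. The SD of C−A is 2σ on T2-to-T3 change and √2σ on T3 levels. The standardised paired differences are therefore 0.308 and 0.636 on change, and 0.435 and 0.900 at T3.

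Simulated paired t tests (40,000 trials per entry) gave the probability that both contrasts are significant and favourable. Each cell shows 0.05/6 versus 0.05 per test:

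| Pattern | Change, λ = 14.16 | Change, λ = 60.48 | T3 level, λ = 14.16 | T3 level, λ = 60.48 |
|---|---|---|---|---|
| Additive | 0.05 vs 0.19 | 0.55 vs 0.83 | 0.16 vs 0.44 | 0.94 vs 0.99 |
| Half-additive (C = 1.5d) | 0.01 vs 0.07 | 0.14 vs 0.39 | 0.03 vs 0.15 | 0.44 vs 0.75 |
| Only C works | 0.27 vs 0.59 | 0.99 vs 1.00 | 0.70 vs 0.92 | 1.00 vs 1.00 |

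These figures do not also require the interaction to be significant first.

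**4. Detectable difference for H3.** For 80% joint power with equal contrasts, the paired difference must be 0.61 SD at 0.05 each or 0.77 SD at 0.05/6 with 28 completers. With 35 it is 0.55 or 0.68. These do not depend on either calibration in step 3.

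**The case against.** The strongest reply is that a power shortfall cannot be read from the documents. The λ = 14.16 calibration sets aside the stated f = 0.30 and shrinks the effect until the crossover interaction has just 0.80 power. Taken literally in a within-subject design, f = 0.30 gives λ of about 60, and H3 power with Bonferroni then runs from about 0.14 to 1.00 by pattern and endpoint. This stands. A reader might infer that H3 power is far below 0.80, or that the trial would usually miss a true H3. The documents give no pairwise effect, SD or correlation that would support either statement. They support only that H3 power is unstated and may be well below 0.80.

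Two other readings also go too far:
- **That H3 is the question in the title.** The title names the effects of the combination, not its superiority over each component. H3 is one of three hypotheses, though the only one about the combination.
- **That Bonferroni protects against nothing, or that the plan over-controls error.** The same post-hoc family serves H1 and H2, and its size is undefined. There is no correction across the six listed outcomes, so overall multiplicity is under-controlled. The point about Bonferroni holds only for the H3 pair within one outcome.

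It is also fair that relaxing alpha for this pair, with no named outcome or endpoint, would give H3 one unadjusted chance per marker. The fix has to close that gap.

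**Conclusion.** The point holds in limited form. H3 needs two contrasts, and the plan gives neither a decision rule nor a power figure for them. Bonferroni between those two is unnecessary for H3 within one outcome.

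How much power this costs depends on assumptions the documents do not settle. For additive effects on change, Bonferroni takes H3 power from 0.19 to 0.05 under one calibration and from 0.83 to 0.55 under the other. The cost is negligible if only the combination works and f = 0.30 is literal. The loss of 0.16 SD in detectable difference (0.77 against 0.61 with 28 completers) needs neither calibration, but assumes equal contrasts, independent residuals and a six-pair family.

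The plan should be changed because the remedy is cheap and settles in advance what counts as support for H3.

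**What to change.** **Statistical Analysis.** Name one primary outcome and add, in substance: *H3 is supported only if C−A and C−B on the T2-to-T3 change are both in the favourable direction with two-sided p < 0.05 each (intersection-union test); no Bonferroni adjustment is applied between these two. If only one is met, H3 is not supported.* Keep Bonferroni for the other pairs and state how many pairs its family contains. Label H3 results on all other outcomes secondary or exploratory.

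**Sample-size paragraph under Method.** State that 0.80 refers to the omnibus interaction calculation and not to H3. Give the difference detectable for H3 with 28 completers: about 0.61 SD of the paired difference in the chosen endpoint for 80% joint power, assuming equal contrasts and independent residuals. In the same edit, reconcile the within-between option with the fully within-subject design, and the four time levels with the three measurement times described.

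**Cost.** A few sentences, and no extra participants or data. A single significant contrast can no longer be called support for H3, and the stated figure is less favourable than 0.80 appears.

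### The aim of examining whether the interventions shorten recovery time cannot be met with one post-intervention assessment; the design supports a claim about the degree of recovery at T3

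*Combined protocol and SAP*

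**What the plan says.** The aim appears twice. Under Objective it is a purpose, "with the goal of shortening recovery time and preventing performance decline following intensive exercise". In the opening of the Method section it becomes something the study will examine: "whether these interventions can shorten recovery time and prevent performance decline after prolonged and intense exercise".

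The research question names three occasions: "immediately before, immediately after a 10-kilometer (10K) run, and following a 20-minute recovery intervention". The Experimental Sessions section matches this. T1 is taken before the run. For T2, "Immediately after completing the 10K run, the procedures conducted in Test 1 will be repeated". The intervention follows and lasts 20 minutes in every condition. For T3, "The procedures conducted in Test 1 will be repeated immediately after the participant completes the assigned intervention protocol". Sessions are run "with a one-week interval between sessions", and nothing is described between T3 and the next session.

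The dependent variables are two questionnaires, HRV, the Stroop test, vertical jump and MVIC with EMG. None is a time to recovery, and no threshold for having recovered is given. The Statistical Analysis section specifies a repeated measures ANOVA with four levels of time and four groups, and the document closes by promising recommendations for "optimizing performance and minimizing injury risk".

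**The concern.** A study aim sets what the trial may conclude. Time to recovery is a property of the whole course after the run, and one value after the intervention does not fix that course. A favourable T3 contrast shows that more of the deficit has been regained by that moment. It does not show when recovery is complete, or whether the advantage lasts beyond the test battery.

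The second half of the aim has a timing problem. The fall from T1 to T2 is complete before any condition is applied, so no condition can prevent that fall. Only what is left of it at T3 can differ between conditions.

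The closing sentence adds injury risk, for which no outcome is listed. The document sets no estimand and no limit on interpretation, so a positive T3 result could be written up against the broader aim.

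**Working it through.** **What each part of the aim needs, against what is described**

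| Aim | What it needs | What the document describes |
|---|---|---|
| Shorter recovery time | A recovery criterion and repeated assessments until it is met | One assessment (T3), no criterion |
| Prevented decline, meaning the T1-to-T2 fall | Intervention before or during the run | Intervention after T2 |
| Prevented decline, meaning residual deficit at T3 | T1, T2 and T3 in each condition | Available |
| H1–H3 and the specific aims (marker levels) | T2 and T3 in each condition | Available |
| Lower injury risk | An injury outcome | None listed |

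**Interval between T2 and T3.** T2 and T3 both repeat the T1 procedures. If their order is kept, the gap between the T2 and T3 values of any one measure is the length of one battery plus the intervention. The only stated battery times are 5 minutes of HRV recording and three jumps one minute apart (2 minutes). The gap is therefore at least 5 + 2 + 20 = 27 minutes. Questionnaires, Stroop, EMG fitting, MVIC and device set-up lengthen it by unstated amounts.

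**One condition, one T3 value (assumed: 60% of the T1-to-T2 deficit remains at 27 minutes).** Time from T2 to 95% recovery:
- Linear course: 0.95 × 27 / 0.40 = 64 minutes.
- Exponential course: τ = −27 / ln(0.60) = 52.9; time = τ × ln(20) = 52.9 × 2.996 = 158 minutes.
- Course that levels off with 10% of the deficit remaining: 95% recovery is never reached.

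All three agree with the same T1, T2 and T3.

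**Two conditions (assumed fractions remaining; exponential course; 27 minutes).** Time to 95% recovery is −27 × ln(20) / ln(r):

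| r | Minutes |
|---|---|
| 0.70 | 226.8 |
| 0.60 | 158.3 |
| 0.50 | 116.7 |
| 0.40 | 88.3 |

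- 60% (rest) versus 50% (treated): 158.3 − 116.7 = about 42 minutes saved.
- 50% versus 40%: 116.7 − 88.3 = about 28 minutes.
- 70% versus 60%: 226.8 − 158.3 = about 68 minutes.

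If the advantage fades after the T3 battery and the treated course rejoins the resting one, the saving is 0 in each case, with the same data. The minutes grow in proportion to the T2-to-T3 interval, so a longer battery raises the upper figures and leaves the lower one at 0.

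**Does the sample size point to a fourth assessment?** The stated n = 28 (f = 0.30, α = 0.05, power 0.80) reproduces for a within-between interaction with four groups, four measurements, correlation 0.5 and no sphericity correction (power 0.863 at 28). Three measurements with the other inputs unchanged give 32, and power 0.789 at 28. Several other combinations of unstated inputs also give 28; two groups, three measurements and correlation 0.3 is one. The figure therefore does not show that a fourth time point was planned, and the present point does not depend on it.

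**The case against.** The strongest reply is that the tested content already fits the design. The research question names exactly the three occasions, and H1–H3 and all five specific aims concern marker levels. The Objective's wording is a motivation, so the mismatch rests mainly on one sentence in the Method section. This largely stands, and it keeps the point modest. It does not remove that sentence, which says the study will examine recovery time.

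Four stronger readings are tempting and should not be drawn:

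- **That the trial cannot answer its hypotheses.** It can. T3 compared with passive rest, given T2, addresses recovery of the markers.
- **That preventing decline is unanswerable on any reading.** The document speaks of decline after exercise and does not define it as T1 to T2. Read as deficit still present at T3, it is testable, although attenuation or early restoration describes it better.
- **That an effect ending when the device comes off would give the same T3 data.** For jump and MVIC this is not supported. If the T1 order is kept, the first jump comes more than 5 minutes after the device stops and MVIC more than 7 minutes after, so such an effect would probably not appear in them. What remains is narrower: a gain lost after T3 would go undetected.
- **That a T3 difference will be reported as shorter recovery time.** No section sets such a rule. The aim only leaves it open.

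It may also be said that four time levels in the ANOVA imply a later assessment. None is described, and a fourth point would still need a stated time and a recovery criterion before it could support a recovery-time claim.

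**Conclusion.** The point holds for recovery time: with one described post-intervention assessment and no recovery criterion, it is not identified. For prevention of decline, the aim holds only in the sense of a smaller residual deficit at T3. The marker-level hypotheses are unaffected.

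The ranges of 0 to about 28, 42 or 68 minutes illustrate the ambiguity and are not estimates. They rest on assumed fractions remaining, an assumed exponential course and the minimum interval of 27 minutes with the T1 test order kept. The conclusion needs none of these values. It would change only if later assessments and a recovery criterion were planned but left out of the document, which is why the discrepancy between four and three time points must be settled. The correction is worth making because it is cheap and limits the conclusions to what the data can show.

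**What to change.** 1. Under Objective and in the opening of the Method section, restate the aim as the degree of recovery at T3, after the 20-minute intervention, compared with passive rest.
2. In the Statistical Analysis section, make the main contrast the within-participant difference between conditions in T3, adjusted for the same session's T2. Report T3 minus T1 with a 95% confidence interval in each condition as the residual deficit.
3. State that no conclusion will be drawn on time to recovery or injury risk, and bring the closing sentence into line.
4. Reconcile the four time levels in the ANOVA with T1, T2 and T3.

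The cost is a narrower claim and a small change to the analysis, since the T2-adjusted contrast replaces the planned interaction as the main comparison. T2 is already collected in every session, so no visits or measurements are added. If recovery time itself is wanted, later assessments at stated times and a recovery criterion would have to be specified before data collection, which would add measurements.

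### The crossover is to be analysed by a Time × Group ANOVA with no period terms, no stated sequence balance, no rule for missed sessions, and four levels of Time where three are measured

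*Combined protocol and SAP*

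**What the plan says.** All references are to the combined protocol and SAP.

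- **Design (Method).** The trial is a "crossover trial using a mixed experimental design". Every runner takes four protocols one week apart. Randomization works by "assigning participants to one of four sequences". One example sequence is given; the other three are not listed and balance over periods is not stated. The intention is clear: "Each participant will experience all protocols, allowing within-subject comparisons".
- **Sample size (Method, participants paragraph).** The calculation is for "repeated measures ANOVA with within-between interaction" with f = 0.30, α = 0.05 and power 0.80, giving 28. Then: "Accounting for potential dropouts, 35 participants will be recruited".
- **Missed sessions (same paragraph).** "Participants may withdraw voluntarily, fail to attend sessions, or be removed". No rate is given, and no rule for analysing a runner with two or three attended sessions.
- **Measurement times (Experimental Sessions).** There are three: T1 before the run, T2 after it, and "Post-intervention Measurements (T3").
- **Analysis (Statistical Analysis).** The only model is a Time × Group repeated measures ANOVA in SPSS 29, with four levels of each factor and Bonferroni follow-up tests. Period is not mentioned.

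**The concern.** Three features of the design do not reach the analysis.

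1. **Period.** Sessions are weeks apart, so weather, training state and practice can shift results from one session to the next. "Participants will also complete a familiarization session with the 10K course", which should reduce practice effects but not week-to-week ones. A shift that is equal at T1, T2 and T3 drops out of Time × Group. A shift in how much runners tire or recover does not. Whether that costs only precision or produces false positives depends on sequence balance, which the plan leaves open.
2. **Missed sessions.** With condition and time both within runner, the ANOVA needs every cell. One missed session then discards the runner's other sessions, each of which includes a 10K run. This is an inference: the mixed-design label and the sample-size method leave the status of Group unclear. Entering Group as between-runner would avoid the loss but ignore the pairing that the design is built on.
3. **Time.** A factor with four levels cannot be fitted to three measurement times.

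**Working it through.** **1. The plan's own figure.** For a within-between interaction with k groups and m times, λ = f²·N·m/(1−ρ), with df (k−1)(m−1) and (N−k)(m−1). The plan states neither ρ nor ε; assume ρ = 0.5 and ε = 1.
- k = 4, m = 4: the smallest N is 25, or 28 in equal groups. At 28, λ = 0.09×28×4/0.5 = 20.16 and power is 0.863. This is one setting that returns 28, and it treats Group as between-runner.
- k = 4, m = 3: λ = 15.12 and power at 28 is 0.789. The smallest N is 29, or 32 in equal groups.
- Dropout: 28/(1−0.20) = 35.

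**2. Sequence balance.** Four conditions have 24 orders, so there are 10,626 sets of four distinct sequences. Only 24 of these put each condition once in each period. That is not a probability of imbalance, since nobody need choose at random, but it shows that balance must be stated.

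Take one unbalanced set that includes the plan's example: BADC, BDAC, ABDC, BACD, allocated 9/9/9/8. Mean period positions are:
- A: (18+27+9+16)/35 = 2.00
- B: (9+9+18+8)/35 = 1.26
- C: (36+36+36+24)/35 = 3.77
- D: (27+18+27+32)/35 = 2.97

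A drift of 0.2 SD per week then biases C minus B by 0.2 × (3.77−1.26) = 0.50 SD. In a period-balanced set with equal allocation every condition averages 2.5, so this bias is absent.

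**3. Drift in the T3−T2 change.** Simulated with 35 complete runners and no period terms. Drift is in SD of the change per week and is assumed.

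| Drift | Power, Williams square (80% without drift) | Type I error, one unbalanced set |
|---|---|---|
| 0.1 | about 79% | about 14% |
| 0.2 | about 78% | about 45% |
| 0.3 | about 74% | about 83% |

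For the set in step 2, drifts of 0.25 and 0.5 residual SD gave type I error of 0.62 and 1.00 without period and about 0.05 with it.

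**4. Missed sessions.** The miss rate m per session is assumed.
- Complete runners: 35(1−m)⁴.
- Allowance used up when 35(1−m)⁴ = 28, so m = 1−(28/35)^(1/4) = 5.4%.
- A runner with k sessions keeps (k−1)/3 of a complete runner's within-runner information on Time × Group.
- Equivalent runners, sporadic misses: 35[4(1−m)−1+m⁴]/3.
- Equivalent runners, permanent dropout: 35[(1−m)⁴ + (2/3)m(1−m)³ + (1/3)m(1−m)²].
- Power: noncentral F for three times, df 6 and 6(n−1), with λ = 14.16·n/28, which gives 80% at 28 complete runners.

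| m | Complete-case ANOVA: runners (power) | All sessions, sporadic | All sessions, permanent |
|---|---|---|---|
| 3% | 31.0 (0.85) | 33.6 (0.88) | 32.0 (0.86) |
| 5% | 28.5 (0.81) | 32.7 (0.87) | 30.0 (0.83) |
| 10% | 23.0 (0.70) | 30.3 (0.84) | 25.6 (0.76) |

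**5. Whether the replacement model can do harm.** Simulations at full attendance, with assumed variances:
- *Runner-by-time term left out* (variances: runner 0.5, session 0.2, residual 0.3, runner-by-time 0.10): power is 58.4%, against 79.0% for both the ANOVA and the model that has the term.
- *Unequal residual variances* (0.10/0.30/0.50 at T1 to T3): the Greenhouse-Geisser ANOVA has 69.8% and an unstructured-covariance model 67.4%. With 5% permanent dropout the figures are 60.6% and 59.4% (500 draws).

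**The case against.** **Dropout is already allowed for.** This stands. The step from 28 to 35 covers about 5.4% missed per session. A reader might infer that the trial is underpowered because the ANOVA discards runners. The documents do not support that: with 80% set at 28, the complete-case ANOVA still has 0.81 at 5% missed. Setting 80% at 35 instead would make planned-for loss look like a shortfall. Nor are these powers forecasts, because 28 reproduces as a between-group calculation; only the differences between analyses are informative.

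**Period cancels from the planned interaction.** This is true only of a drift equal at all three times. Two opposite over-readings are tempting. One is that leaving period out costs efficiency and never causes bias, which needs balanced sequences that the plan does not state. The other is that the results will be biased. That is not shown either: the aim of limiting order effects is stated, and the four sequences may well be balanced.

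**A mixed model may gain little.** This stands in part. The listed exits are mainly withdrawal and removal, which are permanent, and there the gain at 5% is only 0.81 to 0.83. If an unstructured covariance is needed, no gain was demonstrated in that case. A reader should not infer that the model recovers the whole loss.

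**The Time mismatch and the status of Group are separate defects.** Agreed. They must be settled before any model can be fitted, but they add nothing to the sizes above.

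**Conclusion.** The point holds as a cheap improvement, with one element wrong as written: the four-level Time factor does not match T1 to T3.

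- **Period.** A drift in the response costs little under balanced sequences (80% power falls to about 74% at 0.3 SD per week). It can badly inflate type I error under unbalanced ones (about 14 to 83% over the assumed range, for one set). The exposure is conditional on unlisted sequences and on drifts for which the documents give no figure.
- **Missed sessions.** The efficiency loss is moderate: about 0.02 to 0.06 in power at 5% missed and 0.06 to 0.14 at 10%. The attendance gain is zero with full attendance. It rests on condition being within-runner, on assumed miss rates, on equal variances over time and on sessions missing at random. Removal for intolerance of a device could break the last assumption, and could make the complete cases selective too.

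**What to change.** 1. List four period-balanced sequences (a Williams square) and block the allocation. Balance and period terms are both needed: in one scenario, adding period to an unbalanced set restored the type I error but left power at about 0.79, against 0.89 with a Williams square.
2. State that condition is a within-runner factor, and make the levels of Time match the measured times.
3. Replace the ANOVA with a linear mixed model in SPSS on all attended sessions. Fixed effects: condition, time, condition × time, period and period × time. A period main effect alone does nothing for the planned test. Random effects: runner, session within runner, and runner-by-time. Use small-sample (Satterthwaite or Kenward-Roger) degrees of freedom. If equal variances over time cannot be assumed, prespecify an unstructured covariance over time at runner and session level.
4. Keep condition × time as the planned test, with Bonferroni-adjusted contrasts.
5. Report the reasons for missed sessions by condition.

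Cost: SAP wording, a few degrees of freedom, the missing-at-random assumption, and about 1 to 2.5 power points in simulation if the covariance is unstructured. No extra runners, visits or software.
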